10.1.8 Visit 7: End-of-Treatment/Week 24 (or Early Termination)

The End of treatment visit is scheduled for Week 24. If a patient discontinues treatment before Week 24, a premature EOT (as noted in the e-CRF) visit will be performed employing all assessments and procedures associated with Visit 7/EOT.

- Questionnaires/forms to be completed:
 - SHAQ (by patient)
 - UCLA SCTC GIT 2.0 (by patient)
 - EQ-5D-5L (by patient)
 - Patient Global Assessment (by patient)
 - Physician Global Assessment (by Investigator)
- Record all concomitant medication use
- Inquire about AEs/SAEs
- Inquire about Resource Utilization (Refer to [Section 9.3.2](#))
- Assess for Step 1 of CRISS (cardiopulmonary and/or renal involvement)
- Review patient booklet to assess local tolerability at the injection site and treatment compliance
- Record vital signs including BP, heart rate and weight

- Perform a complete physical examination (Refer to [Section 9.2.2.1](#)), including:
 - Perform the mRSS
 - Perform a TJC28
 - Perform a digital ulcer count
- Perform 12-lead ECG
- Blood and Urine Testing
 - Obtain blood samples for complete clinical laboratory determinations including hematology and biochemistry profile
 - Obtain urine for urinalysis (dipstick)
 - For women of child bearing potential:
 - Perform urine pregnancy test. The patients should be instructed to do the urine pregnancy test at home on a monthly basis during the intervals in between on-study visits for the duration of the study. In case of a positive pregnancy test, the patient should be advised to contact immediately the Investigator
 - Dispense urine pregnancy test kits for monthly urine pregnancy tests (2 months supply)
 - Obtain blood sample for serum SAR156597 level (PK) and for anti-SAR156597 antibody (ADA)
 - Obtain blood sample for ANCA and complements (C3, C4 and CH50)
 - Obtain blood samples for protein biomarkers analysis
- Perform PFTs: observed and % predicted FVC, and observed and % predicted DLco (corrected for hemoglobin)
- Call IVRS to update the patient's status (EOT)
- Schedule an appointment for a phone call for Week 30
- Schedule an appointment for next visit, Visit 8 (EOS visit).

Post treatment, the patients will be observed for 11 weeks in a follow-up period. It will consist on one follow-up phone call at Week 30 and EOS visit at Week 35 (Visit 8).

10.1.9 Phone call: Follow-up post treatment/Week 30

The patient will be contacted over phone to:

- Record all concomitant medications
- Inquire about AEs/SAEs
- Ask about the result of pregnancy test from Week 28.

10.1.10 Visit 8: End-of-study visit/Week 35

- Questionnaires/forms to be completed:
 - SHAQ (by patient)
 - UCLA SCTC GIT 2.0 (by patient)
 - EQ-5D-5L (by patient)
 - Patient Global Assessment (by patient)
 - Physician Global Assessment (by Investigator)
- Record all concomitant medication use
- Inquire about AEs/SAEs
- Ask about the result of pregnancy test from Week 32
- Inquire about Resource Utilization (Refer to [Section 9.3.2](#))
- Assess for Step 1 of CRISS (cardiopulmonary and/or renal involvement)
- Record vital signs including BP, heart rate and weight
- Perform a complete physical examination (Refer to [Section 9.2.2.1](#)), including:
 - Perform the mRSS
 - Perform a TJC28
 - Perform a digital ulcer count
- Perform 12-lead ECG
- Blood and Urine Testing
 - Obtain blood samples for complete clinical laboratory determinations including hematology and biochemistry profile
 - Obtain urine for urinalysis (dipstick)
 - Perform urine pregnancy test for women of childbearing potential
 - Obtain blood sample for serum SAR156597 level (PK) and for anti-SAR156597 antibody (ADA)
 - Obtain blood sample for ANCA and complements (C3, C4 and CH50)
 - Obtain blood samples for protein biomarkers analysis
 - Obtain blood samples for future protein assays and mRNA analysis (only for those patients who have signed a separate Future Use of Samples informed consent form)
- Perform PFTs: observed and % predicted FVC, and observed and % predicted DLco (corrected for hemoglobin)
- Call IVRS to update the patient's status (study completion).

10.2 DEFINITION OF SOURCE DATA

All evaluations that are reported in the e-CRF and in the patient booklet (completed by the nurse) must be supported by appropriately identified source documentation.

10.3 HANDLING OF PATIENT TEMPORARY OR PERMANENT TREATMENT DISCONTINUATION AND OF PATIENT STUDY DISCONTINUATION

The IMP should be continued whenever possible. In case the IMP is stopped, it should be determined whether the stop is temporary; permanent IMP discontinuation should be considered as the last resort. Any IMP discontinuation should be fully documented in the e-CRF. In any case, the patient should remain in the study as long as possible.

10.3.1 Temporary treatment discontinuation with investigational medicinal products

Temporary treatment discontinuation may be considered by the Investigator because of suspected AE(s). Re-initiation of treatment with the IMP will be considered with close and appropriate clinical and/or laboratory monitoring after the Investigator has determined according to his/her best medical judgment that the causality of the event was unlikely related to the IMP(s) and if the selection criteria for the study are still met (refer to [Section 7.1](#) and [Section 7.2](#)).

For example, suspicion of vasculitis should lead to a temporary discontinuation to allow for a thorough diagnostic work-up and evaluation.

A discontinuation of IMP greater than 30 days will be considered permanent and relevant e-CRF sections should be populated.

10.3.2 Permanent treatment discontinuation with investigational medicinal product(s)

Permanent treatment discontinuation is any treatment discontinuation associated with the definitive decision from the Investigator, Sponsor or the patient not to re-expose the patient to the IMP at any time.

10.3.3 List of criteria for permanent treatment discontinuation

The patients may decide to permanently withdraw from treatment with the IMP at any time and for any reason; this decision may also rest with the Investigator or Sponsor. All efforts should be made to document the reason(s) for treatment discontinuation in the e-CRF.

IMP will be permanently discontinued in case of the following events (refer to [Section 10.6](#) for details). The list is a guide and not intended to be exhaustive:

- [REDACTED]
- Symptoms of severe hypersensitivity or anaphylactic reactions (see [Appendix I](#) for definition)
- Severe skin reactions local to the site of IMP injection (see [Appendix J](#))

- Pregnancy
- Any AEs, per Investigator's judgment, that may jeopardize the patient's safety
- Any code breaking requested by the Investigator will lead to permanent treatment discontinuation.
- Any laboratory abnormalities per the algorithms of [Appendix K](#)
- At the specific request of the Sponsor

Any abnormal laboratory value or ECG parameter will be immediately rechecked for confirmation before making a decision regarding of possible permanent IMP discontinuation for the concerned patient. All efforts should be made to reassess in a clinically relevant timeframe (using either local or central lab), the clinical significance of lab abnormalities and corrective actions before making a decision of permanent discontinuation of the IMP for the concerned patient.

10.3.4 Handling of patients after permanent treatment discontinuation

Patients will be followed according to the study procedures as specified in this protocol through the scheduled date of study completion, or through the recovery or stabilization of any AE to be followed as specified in this protocol, whichever comes last.

After permanent discontinuation of treatment, the patients will be assessed using the procedures normally planned for EOT visit/Visit 7 (labeled as Premature/Early EOT in the e-CRF), and then will be asked to come for the remaining on-site visits per schedule (including Visit 7 at Week 24 and EOS at Week 35 for safety monitoring and efficacy assessments, particularly mRSS, SHAQ, FVC and DLco (corrected for hemoglobin) up to Week 24 as these are the primary and secondary endpoints. Other procedures associated with the remaining visits will also be conducted per study flow chart.

All cases of permanent treatment discontinuation should be recorded by the Investigator in the appropriate pages of the e-CRF when considered as confirmed.

10.3.5 Procedure and consequence for patient withdrawal from study

The patients may withdraw from the study before study completion if they decide to do so, at any time and for any reason. Withdrawal of consent for treatment should be distinguished from withdrawal of consent for ongoing study participation with scheduled visits and from withdrawal of consent for non-patient contact follow-up (eg, medical records check). Patients requesting withdrawal of consent for ongoing study participation with follow-up may jeopardize the public health value of the study.

If possible, and prior to the withdrawal of consent for ongoing study participation, the patients will be assessed using the procedure normally planned for the EOS visit (Visit 8). Then, patients will receive a phone call from Investigators at Week 30 for vital status assessment.

Patients who withdraw from the study should be explicitly asked about the reason and the contribution of any possible AE(s) that led to their decision, and any AE information elicited should be documented. The patient may withdraw consent verbally or in writing. If the consent is withdrawn verbally, the site should document it appropriately. Preferably the patient should withdraw consent in writing and, if the patient or the patient's representative refuses or is physically unavailable, the site should document and sign the reason for the patient's failure to withdraw consent in writing.

All study withdrawals should be recorded by the Investigator in the appropriate screens of the e-CRF and in the patient's medical records when considered as confirmed. In the medical record, at least the date of the withdrawal and the reason should be documented.

For patients who did not withdraw consent for ongoing study participation but fail to return to the site, the Investigator should make the best effort to contact the patient (eg, contacting patient's family or private physician, reviewing available registries or health care databases), and to determine his/her health status, particularly vital status. Attempts to contact such patients must be documented in the patient's records (eg, number of attempts and dates of attempted telephone contact and receipt for sending a registered letter).

The statistical analysis plan will specify how these patients lost to follow-up for their primary endpoints will be considered.

Patients who have withdrawn from the study cannot be re-randomized (treated) in the study. Their inclusion and treatment numbers must not be reused.

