	
• Tolerability at the IMP injection site:
- Erythema/redness (diameter and graded severity)- Swelling/induration/edema (diameter and graded severity)- Pain assessment. 
Immunogenicity:
 
• Testing for ADA 
Pharmacokinetics:
 
• SAR156597 plasma concentrations 
Biomarkers:
 
• Measurement of protein biomarkers associated with the activity of the disease (COMP, CCL2) and the IL-4/IL-13 pathway (TARC, periostin, and eotaxin-3).• Archived blood samples for future assays of protein and mRNA biomarkers related to the disease and the response to therapy (requires separate informed consent).
ASSESSMENT SCHEDULE	
The study will comprise 8 on-site visits AND 4 phone calls:
 
• Visits:
- V1 (screening visit) between Day -28 and Day -1.- V2 (baseline visit) at Day 1 (first dosing).- Treatment period: V3 at Week 2, V4 at Week 4, V5 at Week 8, V6 at Week 12, V7 at Week 24.- V8 (End-of-Study [EOS] visit) at Week 35.- A time window of ± 2 days will be allowed for each visit.• Phone calls:
- For safety considerations phone calls will be made at Week 6, 16 and 20 during the treatment period, and at Week 30 during the follow-up period.

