11.4.3 Analyses of safety data

The summary of safety results will be presented by treatment group actually received.

All safety analyses will be performed on the safety population using the following common rules:

- The baseline value is defined generally as the last available value before the first administration of the IMP.
- For quantitative safety parameters based on central laboratory/reading measurements, descriptive statistics will be used to summarize results and change from baseline values by visit and treatment group.
- The analysis of the safety variables will be descriptive and no hypothesis testing is planned.

The following definitions will be applied to laboratory parameters, vital signs, and ECG.

- The potentially clinically significant abnormality (PCSA) values are defined as abnormal values considered medically important by the Sponsor according to predefined criteria/thresholds based on literature review and defined by the Sponsor for clinical laboratory tests, vital signs, and ECG.
- PCSA criteria will determine which patients had at least 1 PCSA during the TEAE period, taking into account all evaluations performed during the TEAE period, including unscheduled or repeated evaluations. The number of all such patients will be the numerator for the TEAE PCSA percentage.

The TEAE period is defined as the time from the first administration of the IMP up to 12 weeks (84 days) from the last dose of IMP.

Please refer to [Section 9.2](#) for the safety endpoints.

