2.1.5.2 Deaths

The deaths observation period are per the observation periods defined above.

- Death on-study: deaths occurring during the on-study observation period.
- Death on-treatment: deaths occurring during the treatment-emergent adverse event period.
- Death post-study: deaths occurring after the end of the study.

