2.4.4.4.8 FVC

Due to the non-normality of the distribution of % predicted FVC, the change from baseline at Week 24, respectively Week 35, will be analyzed using a rank-based analysis of covariance (rank analysis of covariance [ANCOVA]) model adjusted for baseline and stratified on randomization stratum (as per IRT). This model will use the ranks of absolute change from baseline to Week 24 (respectively Week 35) in % predicted FVC as the outcome and the ranks of baseline % predicted FVC as a covariate stratified on the stratification factor (with/without ILD). In case of ties, the mean of the corresponding ranks will be assigned.

The ranking will be done within each stratum of the stratification factor (with/without ILD) in ITT population (both treatment groups combined).

- Missing data due to death will be ranked based on a time-to-death, with shortest time until death as the worst (lowest) rank (from 1 to $n_{\text{stratum, death}}$).
- Absolute change from baseline at Week 24 (respectively Week 35) in % predicted FVC values will be calculated from Week 24 (respectively Week 35) % predicted FVC values and then ranked (from $n_{\text{stratum, death}} + 1$ to n_{stratum}).
- Standardization of ranks using SAS PROC RANK.

Furthermore, the adjustment on baseline % predicted FVC covariate will be done. The residuals from the linear regression of response ranks on baseline ranks will be calculated within each stratum of the stratification factor (with/without ILD).

Finally, treatment effect will be tested using the residuals as scores. The active treatment group will be compared to placebo using a Mantel-Haenszel mean score chi-square test at a one-sided Type-I error level of 5%. This test will be stratified on the stratification factor.

In case of more than 20% of missing data on the % predicted FVC value at Week 24, missing data will be imputed following methods described in [Section 2.5.2](#). Otherwise, the data will not be imputed.

Furthermore, the change in observed FVC from baseline to Week 35 will be analyzed using the MMRM model described in [Section 2.4.4.4](#).

The number of patients with an absolute decreased % predicted FVC from baseline at W24 superior or equal to 5% and respectively 10% will be presented by treatment group.

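### For withdrawn patients last dosed at Weeks 19 to 23, the Week 30 vital-status call falls 7 to 35 days before the on-treatment death window closes

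*Protocol*

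**What the plan says.** **Follow-up after withdrawal (Protocol 10.3.5).** If possible, "prior to the withdrawal of consent for ongoing study participation, the patients will be assessed using the procedure normally planned for the EOS visit". One contact comes after that: "Then, patients will receive a phone call from Investigators at Week 30 for vital status assessment". Active tracing through family, physician or registries is written for a different group: "For patients who did not withdraw consent for ongoing study participation but fail to return to the site, the Investigator should make the best effort". The section treats consent to a medical-records check as separate from consent to visits, but sets no date for such a check.

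**Death windows.** Protocol 11.4.3 ends the treatment-emergent period "up to 12 weeks (84 days) from the last dose of IMP". SAP 2.1.5.2 ties the main death category to it: "Death on-treatment: deaths occurring during the treatment-emergent adverse event period". SAP 2.4.5.2 tabulates on-study, on-treatment and post-study deaths. SAP 2.1.5 ends the on-study period at either the last planned visit or the last study assessment, and does not say which applies to a withdrawn patient. The last planned visit is given in the protocol synopsis: "V8 (End-of-Study [EOS] visit) at Week 35".

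**Rank tests.** In the % predicted FVC analysis at Weeks 24 and 35 (SAP 2.4.4.4.8), deaths take the lowest ranks: "Missing data due to death will be ranked based on a time-to-death". SAP 2.4.4.4.9 applies the same method to % predicted DLco.

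**The concern.** The last visit was evidently placed so that it closes the 84-day window for a patient who takes every dose. The withdrawal call was not. A withdrawn patient last dosed late in the treatment period can die after the call but inside the on-treatment window, and no scheduled step would find the death. It would then be missing from a table that reports on-treatment deaths by arm.

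Safety against placebo is a secondary objective (Protocol 5.2), and Protocol 6.4 justifies the data monitoring committee by the early stage of development in this disease. With 47 patients per arm, a single death in one arm would be noticed, so vital status should be established to the end of the window being reported.

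**Working it through.** **Inputs.** Study day for Week *w* is 7*w* + 1 (target days in SAP Table 3). The last planned dose is at Week 23 (Protocol 1.2, footnote c). The call is at Week 30 (Protocol 10.3.5). The window is last dose + 84 days (Protocol 11.4.3, SAP 2.1.5). Ten-year survival is 70% to 80% (Protocol section 4).

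**Step 1: reproduce the plan's own figure.** SAP 2.1.6 places Week 35 at 12 weeks after the last injection. Week 23 is 7 × 23 + 1 = Day 162, and 162 + 84 = Day 246. Week 35 is 7 × 35 + 1 = Day 246. The two agree exactly.

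**Step 2: on-treatment window after the call.** Week 30 is 7 × 30 + 1 = Day 211. The uncovered part is max(0, 7*w* + 1 + 84 − 211) = 7 × max(0, *w* − 18) days.

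| Last dose | Dose day | Window ends | Days after Day 211 | Share of 84 days |
|---|---|---|---|---|
| Week 18 | 127 | 211 | 0 | 0% |
| Week 19 | 134 | 218 | 7 | 8% |
| Week 20 | 141 | 225 | 14 | 17% |
| Week 21 | 148 | 232 | 21 | 25% |
| Week 22 | 155 | 239 | 28 | 33% |
| Week 23 | 162 | 246 | 35 | 42% |

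The call covers the whole window for last doses at Weeks 0 to 18, which is 19 of the 24 possible last-dose weeks. The other five leave a gap. The ±2-day dosing and visit allowances shift these figures by a few days.

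**Step 3: on-study window.** If a withdrawn patient's on-study period runs to Week 35, 246 − 211 = 35 days are unchecked, whatever the last dose. If it ends at the last assessment, a later death is post-study, and no one is told to look for it. Under the lost-to-follow-up rule in SAP 2.2, a withdrawn patient last reached on Day 211 meets the definition, because 35 days exceeds the 2-day limit.

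**Step 4: Week 35 rank tests.** The Week 35 analysis window is any day after 207 (SAP Table 3). A patient who withdrew before Day 208 has lung-function values only in earlier windows. An undetected death after the call would therefore be an ordinary missing Week 35 value, not a worst rank. The imputation in SAP 2.5.2 is written for Week 24 only.

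**Step 5: size.** With a constant hazard, 80% and 70% ten-year survival give −ln(0.8)/10 = 0.0223 and −ln(0.7)/10 = 0.0357 per year. Over 35 days (35/365.25 year) the risk is 0.0021 to 0.0034 per patient. The documents give no rate of study withdrawal. Assuming 5 to 20 withdrawn patients, all with the full 35-day gap:

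- low end: 5 × 0.0021 ≈ 0.01 deaths
- high end: 20 × 0.0034 ≈ 0.07 deaths

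**The case against.** The strongest reply is that the gap is narrow and partly guarded.

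- **Patients who stop treatment are asked to stay in the study** through Week 35 (Protocol 10.3.4). The on-treatment gap needs a patient dosed at Week 19 or later who also withdraws from the study itself. This stands. However, 19 of 24 weeks is a count of weeks, not of patients. The sample-size section assumes that only 10% stop treatment, so Week 23 should be the commonest last-dose week overall.
- **Other routes may reveal a death.** Known adverse events are followed to recovery, stabilisation or death, if need be beyond the last visit (Protocol 10.4.3). A records check may still be permitted. An SAE after the patient's end of study is reported if the investigator learns of it and attributes it to the drug (Protocol 10.4.4). These help, but none is a scheduled vital-status check.
- **A later call has a price.** It may be harder to complete, and for early withdrawers it lengthens the silent interval. Keeping the Week 30 call removes the second difficulty.

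A reader might infer more than the documents support in two places:

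- **That anyone who withdraws after Week 30 is never contacted.** Such a patient was still on study for the routine Week 30 call and should have end-of-study procedures at withdrawal if possible. Less than 5 weeks is then unobserved. It is true only that 10.3.5 schedules no contact after that withdrawal.
- **That the rank tests mishandle these same patients.** End-of-study procedures include lung function. Done after Day 207, they supply a Week 35 value, so the patient is not missing unless the assessment was not done.

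**Conclusion.** The point holds as a minor gap in safety ascertainment. It is clearest for on-treatment deaths, because that window is fixed by the last dose and does not depend on participation status. For withdrawn patients last dosed at Weeks 19 to 23, the final 7, 14, 21, 28 or 35 days have no scheduled check.

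The on-study part is conditional. It would be tempting to say that the on-study death table requires vital status to Week 35 for every withdrawn patient, but SAP 2.1.5 allows either end date and does not settle it. The rank-test effect follows from the same gap. It is limited to patients who withdrew before Day 208, and it concerns exploratory tests whose p-values are descriptive (SAP 2.4.4.3).

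The expected number of missed deaths is far below one: about 0.01 to 0.07, given a constant hazard, the protocol's survival range and an assumed 5 to 20 withdrawals. The primary mRSS analysis is unaffected. This is a worthwhile, inexpensive improvement and not a threat to the trial's conclusions.

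**What to change.** **Protocol 10.3.5.** Set the vital-status contact, or a records check where consent allows, at the scheduled Week 35 date and not before last dose + 84 days. Apply it to all withdrawn patients, including those who withdraw after Week 30. The second condition matters only when a late last dose carries the window slightly past Day 246. The Week 30 call may be kept as well. If it is replaced, no information on whether a patient died is lost, because status at Week 35 also settles status at Week 30.

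**SAP 2.1.5.** Add one sentence stating which end-of-study date applies to withdrawn patients, so that a later death is classed the same way by everyone.

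**Cost.** A minor protocol amendment with the review that Protocol section 15 requires, one contact about 5 weeks later that may be harder to achieve, and a second call per withdrawn patient if Week 30 is retained.
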